4.2. Clinical Assessment

This assessment includes clinical assessment, levodopa challenge test, video recording, neuroimaging, and neurocognitive ~~and~~ and psychiatric evaluations. The clinical evaluation is performed in the morning, after a 12-hour withdrawal of antiparkinsonian drugs. Assessment data are obtained before and after the operation (medication-off/ -on state and stimulation ~~on~~-on) and include the MDS-UPDRS, Unified dyskinesia rating scale (UDysRS), modified Hoehn & Yahr stage (off/on-state), levodopa equivalent dose, and body weight. Motor assessments are videotaped, and two raters collected independent ratings.

Subjects are instructed to report any adverse event during the course of the study, including pulling (contractions), tingling, blurry vision, double vision, speech changes, or walking problems.

Table 1

Visit	V0 Screen	V1 Enrollment (Randomizatio n and Surgery)	V2 Initial Programming	V3	V4	V5
Time (±5 days)	Week -9 ~Week -5	Week -5	Week 0 /Month 0	Month 3	Month 9	Month 12
Informed consent	X					
Inclusion criteria	X	X				
Exclusion criteria	X	X				
Randomization		X				
Medication	X	X	X	X	X	X
Programming			X	X	X	X
Pre-surgical assessments		X				
UPDRS III, IV		X	X	X	X	X
UDysRS		X	X	X	X	X
PDQ-39		X	X	X	X	X

Cognitive Tests		X			X	X
Adverse Events	X	X	X	X	X	X

5. Sample size and Statistical analysis

5.1 Sample size

According to the sample size estimation method of comparing the mean of two independent samples, 42 subjects are planned to be enrolled in this study. Increase the number of cases according to the 20% dropout rate, and finally enrolled 50 cases. In this study, the change scores of total scores of visit 5 (month 12) UPDRS IV comparation with baseline is the endpoint to use to calculate the sample size. The specific calculation method was as follows:

Use Power Analysis & Sample Size software 11 (SPSS 11) to calculate the sample size. The formula is as follows.

$$n = \text{Ceiling} \left\{ \frac{(Z_{1-\alpha} + Z_{1-\beta})^2 \sigma_d^2}{2\delta_1^2} \right\}.$$

The non-inferiority hypothesis

Primary Outcome Measures

The changes of dyskinesia scores (UPDRS IV, item 32 + item 33)

H0: interleaving stimulation - empirical stimulation < 0.5 score

H1: interleaving stimulation - empirical stimulation \geq 0.5 score

Significance level: $\alpha = 0.025$ (unilateral),

Power: $1-\beta = 0.8$,

Standard deviation of single group: SD = 1.1,

H0 is the null hypothesis, H1 is the alternative hypothesis. After subjects receiving interleaving stimulation, if the mean change scores of UPDRS IV equals or exceeds 0.5 points than that of those patients receiving empirical stimulation, then H0 will be rejected, non-inferiority conclusion can be made when comparing interleaving stimulation group with empirical stimulation group. If H0 can't be reject, the conclusion that the interleaving stimulation group is better than or equivalent to empirical stimulation group can't be reached.

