**Interleaving stimulation improving dyskinesia in Parkinson's
disease: randomized, double-blind, controlled trial**

2022.5.20

Version 1.5

Interleaving stimulation improving dyskinesia in Parkinson's disease: randomized, double-blind, controlled trial

Study protocol

1. Background

The clinical utility of deep brain stimulation (DBS) for the treatment of Parkinson's disease (PD) has been well established; however, there are a variety of adverse events, such as dyskinesia among subthalamic nucleus (STN) DBS recipients due to varied postoperative management. The artificial electrical signals of deep brain stimulation are delivered with four parameters; contact (0~3), frequency (Hertz - Hz), amplitude (voltage or current) and pulse width (microseconds, μ s). It has recently been reported that interleaving stimulation can be used effectively to treat motor symptoms while avoiding side effects.

Dyskinesia

Levodopa-induced dyskinesias (LIDs) are motor complications of Parkinson's disease. LID is characterized by progressive motor disability and may interfere with quality of life.

STN-DBS has also been demonstrated to provoke or exacerbate dyskinesia (stimulation-induced dyskinesia, SID). Previous studies have showed that the proportion of stimulation-induced dyskinesia is as high as 50% to 75%.

Both kinds of dyskinesias have variable phenotypes, including chorea, ballism, dystonia, myoclonus, or combination of any of these movements. SIDs are easily evoked in patients with severe preoperative LIDs.

In general, reducing the dosage of levodopa can improve LIDs post-operation. However, this approach will fail when dyskinesia is the result of stimulation. Available programming, such as interleaving stimulation could improve dyskinesias post-operation.

So, this study is designed as a prospective, **randomized, double-blind, controlled** study to assess putative differences in the effect of interleaving stimulation and empirical stimulation with regards to post-operation dyskinesia control.

2. Study design

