4.1 Efficacy assessments

The primary efficacy endpoints are the changes of dyskinesia scores and the changes of PDQ-39 scores in interleaving stimulation compared to empirical programming modes. *[Time Frame: 3 months and 9 months]*

The secondary endpoints include the changes of UPDRS III scores and the changes of neuropsychological Battery scores in interleaving stimulation compared to empirical programming modes. *[Time Frame: 3 months and 9 months]*

The parameters in primary and secondary endpoints are also tested at baseline (Enrollment). After DBS activation (Month 0), patients are again assessed at Month 3, Month 9 and Month 12 in off-medication/on-stimulation and on-medication/on-stimulation, as shown in table 1. We defined “on-medication” as roughly 60 min after a patient takes

antiparkinsonian medication when both the clinician and the patient indicate that the medication dose is effective.

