5.2 Statistical analysis

All of the statistical tests used bilateral analysis. $P \leq 0.05$ is considered to be statistically significance (excluding special conditions).

Description of quantitative indicators is used to calculate total cases, missing cases, average cases, standard deviation, minimum, maximum, median and the interquartile range.

Description of classification index is used in different groups of cases and percentage.

Full Analysis Set (FAS): this analysis includes all subjects who received any treatment and provided useful value after the baseline stage for analysis. It also includes violators of the research scheme and subjects with incomplete data who left the trial.

Per Protocol Set (PPS): this analysis includes all subjects who completed the research and complied with the scheme without any serious errors. It also includes subjects who quit the trial because of ineffective treatment.

Safety Analysis Set (SAS): this analysis set includes all subjects who enrolled in the trial, received at least one treatment and was used for safety evaluation. Safety information records from all subjects were evaluated, including adverse events and the results of lab examinations.

6. Adverse Event

6.1 definition

Adverse Event : An AE is defined as any untoward medical occurrence, regardless of its relationship to the study device (study suture) or the study procedure. An untoward medical occurrence includes any new, undesirable medical experience or worsening of a pre-existing condition, which occurs at any point from the surgery to Final Visit.

Serious Adverse Event: A Serious Adverse Event (SAE) is any AE that:

- led to a death,
- led to a serious deterioration in the health of the subject that either resulted in:
 - a congenital deformity or abnormality;
 - a life-threatening illness or injury;
 - a permanent impairment of a body structure or a body function;
 - in-patient hospitalization or prolongation of existing hospitalization;
 - medical or surgical intervention to prevent life-threatening illness or injury; or permanent impairment of a body structure or a body function.

Relationship of Adverse Events: It is the Investigator's responsibility to assess the relationship of an AE to the study procedure and study device.

The following guidelines should be used in determining the relationship of an adverse event

to the study device, study procedure, or other causality:

- NOT RELATED: The event is due to extraneous causes.

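### Section 5.2 names no model for the primary outcomes, and the only between-arm comparison described, an unadjusted difference in mean change, makes no covariate use of the enrolment scores already collected

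*Combined protocol and SAP*

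**What the plan says.** Sections 2.2 and 4.1 define the primary outcomes as changes in the dyskinesia score (UPDRS IV items 32 + 33) and in PDQ-39, with time frames of 3 and 9 months. Section 5.1 sizes the trial "According to the sample size estimation method of comparing the mean of two independent samples". It bases the decision on the mean change in UPDRS IV in one arm compared with the other, and uses total UPDRS IV at Month 12 against baseline as the sizing endpoint.

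Section 5.2 states that "All of the statistical tests used bilateral analysis", sets a P threshold of 0.05, lists descriptive statistics and defines three analysis sets. It names no test, model or covariate for any endpoint.

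On what is collected, section 4.1 says "The parameters in primary and secondary endpoints are also tested at baseline (Enrollment"), and Table 1 schedules UPDRS III, UPDRS IV and PDQ-39 at enrolment, Month 0, Month 3, Month 9 and Month 12. The Background says that "SIDs are easily evoked in patients with severe preoperative LIDs". Section 3.1 describes 1:1 allocation in pairs by order of enrolment and mentions no stratification on dyskinesia severity.

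**The concern.** The protocol itself treats starting dyskinesia as prognostic, and the score is measured before randomized treatment begins. Neither the allocation nor any stated analysis controls for it. The one comparison that is described subtracts the baseline in full, which is the best use of it only if follow-up rises one-for-one with baseline. If the slope is lower, the subtraction adds noise, and an arm that happens to start with worse dyskinesia will tend to show a larger fall for that reason alone. With about 21 analysed patients per arm, both effects matter. Because 5.2 names no model, the choice between adjusted and unadjusted analysis could also be made after the data are seen.

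**Working it through.** **Inputs from section 5.1.** Distance 0.5 points ("H0: interleaving stimulation - empirical stimulation < 0.5 score"); "Standard deviation of single group: SD = 1.1"; one-sided alpha 0.025; power 0.80; 42 evaluable patients, so 21 per arm. The plan does not say whether 1.1 is the SD of the change or of the raw score; it is taken here as the SD of the change. **Not in the documents:** the correlation rho between enrolment and follow-up scores (varied from 0.3 to 0.9) and the ratio of the two SDs (taken as 1, then tested).

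**The plan's own figure.** Two independent means need n per arm = 2 × 1.1² × (1.960 + 0.842)² / 0.5² = 2 × 1.21 × 7.849 / 0.25 = 75.98, so 76 per arm or 152 in total, not 42. The printed formula with sigma_d = 1.1 gives 1.21 × 7.849 / (2 × 0.25) = 18.99, so 19. Its t-based version gives 20.002, so 21, and 2 × 21 = 42. That route treats the single-group SD as the SD of within-patient differences, which does not fit parallel arms.

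**Precision.** With a common SD s at both visits:
- variance of a change score: 2s²(1 − rho)
- residual variance under ANCOVA: s²(1 − rho²)
- ratio: (1 + rho)/2
- small-sample price of one covariate at N = 42: about 1 + 1/(42 − 4) = 1.026

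The power column uses the noncentral t with 21 per arm, a distance of 0.5 and SD 1.1 × √(net ratio). The unadjusted comparison has 40 degrees of freedom and ANCOVA has 39.

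| rho (assumed) | (1 + rho)/2 | net of covariate | variance saved | relative CI width | power at 0.5 |
|---|---|---|---|---|---|
| unadjusted | 1 | 1 | – | 1 | 0.30 |
| 0.3 | 0.65 | 0.667 | 33% | 0.82 | 0.42 |
| 0.5 | 0.75 | 0.770 | 23% | 0.88 | 0.37 |
| 0.7 | 0.85 | 0.872 | 13% | 0.93 | 0.34 |
| 0.9 | 0.95 | 0.975 | 2.5% | 0.99 | 0.31 |

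Break-even is at rho = 2/1.026 − 1, about 0.95. By the normal approximation, 80% power at 0.5 points would need 50, 57, 65 or 73 per arm with ANCOVA for these four values of rho, against 76 unadjusted.

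**Chance imbalance.** With equal variances the regression slope is rho, so a baseline difference D between arms shifts the change-score estimate by (1 − rho)D in size. If 1.1 is the SD of the change, then s = 1.1/√(2(1 − rho)). An imbalance of one standard error is D = s√(2/21), so the shift is 1.1 × √((1 − rho)/2) × √(2/21). For rho 0.3, 0.5 and 0.7 this is 0.20, 0.17 and 0.13 points, or 40%, 34% and 26% of the 0.5-point margin. For rho 0.9 it is 0.08 points, or 15%.

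**If the variances differ.** Let k be the follow-up SD divided by the baseline SD. The slope is rho × k and the variance ratio is k²(1 − rho²)/(1 + k² − 2 rho k). With rho 0.7 and k 1.5, the slope is 1.05 and the ratio is 2.25 × 0.51 / (1 + 2.25 − 2.1) = 1.1475/1.15 = 0.998. There is then no gain, and the covariate costs its 2.6%.

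**The case against.** The strongest objection is that the plan never prescribes an unadjusted test. A reader might infer one from 5.1, but sizing by two independent means does not commit a trial to analysing that way, and 5.2 is silent. This stands. What the documents support is that no model is specified and that the one comparison described is unadjusted.

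A second objection is that a change-score comparison is unbiased over randomization, so nothing is invalid. This also stands: the point concerns precision and the estimate conditional on the imbalance that occurs.

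Third, the gain depends on a correlation the documents do not give and on equal variances, which may not hold across surgery and activation. A reader might take ANCOVA to be clearly better and free of cost. Neither follows: the saving runs from 33% to 2.5% over the range shown and can vanish, and each covariate has a price.

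Fourth, Month 3 looks like the natural baseline, since interleaving is barred until then (section 3.2). But randomization precedes implantation, the programmer knows the allocation (section 3.1), stimulation and medication are adjusted on clinical need over those months, and Month 3 falls within the stated outcome time frame. Masking of patient and rater limits the risk without removing it. The documents therefore do not support Month 3 as the main covariate.

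Finally, the endpoint is itself unsettled (Months 3 and 9 in 2.2 and 4.1, total UPDRS IV at Month 12 in 5.1). That must be resolved first, but it is no reason to leave the model open.

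**Conclusion.** The point holds as a gap in specification with an available improvement, not as an error that invalidates the trial. No primary model is named, the only described comparison is unadjusted, and a pre-randomization score that the protocol regards as prognostic is already collected. ANCOVA on the enrolment score would be expected to cut variance by about 13% to 33% for rho 0.7 to 0.3, and by about 2.5% at 0.9. These figures assume equal variances, one covariate and 42 analysed patients. The likely downside is small, about 2.6% of variance if the covariate brings nothing.

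A reader might infer that adjustment would rescue the power of the trial. It would not: at the protocol's own 0.5 points, power moves from about 0.30 to between 0.31 and 0.42. The sample size in 5.1 needs its own correction.

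**What to change.** First reconcile the primary endpoint: sections 2.2 and 4.1 against the Month 12 total UPDRS IV used in 5.1. Then state in 5.2 that each primary outcome at Month 9 is analysed by ANCOVA with arm as factor and the enrolment score of the same measure as covariate, reporting the adjusted difference with its 95% CI. With that covariate in the model, using the Month 9 score or its change from enrolment gives the same arm estimate. Use the same model for UPDRS III.

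Add a sensitivity analysis that also adjusts for the Month 3 score. State that this score is measured after randomization while the programmer knows the allocation, and say how patients without a Month 3 score are handled.

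State the correlation assumed when the sample size is recalculated with a parallel-group formula. The analysis change needs wording only and no new data. It costs one degree of freedom in the main model and a second in the sensitivity analysis, where two covariates cost about 2/37 = 5.4% of variance before any gain.

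### Section 5.1: the hypotheses do not express the non-inferiority they are labelled with, and the 42 patients and 80% power do not follow from the stated two-sample method and inputs

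*Combined protocol and SAP*

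**What the plan says.** All of the sizing text is in section 5.1 of the combined protocol and SAP.

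- **Method and size.** The plan uses a "sample size estimation method of comparing the mean of two independent samples, 42 subjects are planned to be enrolled". Section 3.1 confirms a 1:1 parallel design with 25 patients per arm.
- **Inputs.** "Standard deviation of single group: SD = 1.1", one-sided alpha 0.025, power 0.8.
- **Formula.** The squared sum of the two normal quantiles, times sigma_d squared, divided by twice delta_1 squared. Neither sigma_d nor delta_1 is defined.
- **Hypotheses.** Under a non-inferiority heading, and for the sum of items 32 and 33: "H0: interleaving stimulation - empirical stimulation < 0.5 score". The alternative is a difference of 0.5 or more.
- **Decision rule.** The null is rejected "if the mean change scores of UPDRS IV equals or exceeds 0.5 points than that of those patients receiving empirical stimulation", and then a "non-inferiority conclusion can be made when comparing interleaving stimulation group with empirical stimulation group".
- **Endpoint used for sizing.** "the change scores of total scores of visit 5 (month 12) UPDRS IV comparation with baseline is the endpoint".
- **Dropout.** "Increase the number of cases according to the 20% dropout rate, and finally enrolled 50 cases".

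Section 5.2 says "All of the statistical tests used bilateral analysis", with a significance level of 0.05 apart from unspecified special conditions. It names no test for the primary endpoint and no comparison with a margin. No assumed true difference between the arms is given anywhere.

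**The concern.** A non-inferiority null says that the new treatment is worse than the control by at least the margin. The printed null does not say this under either sign convention, so the rule for a primary outcome contradicts the conclusion drawn from it. Separately, the formula is not the one for the named method and no true difference is stated, so the 80% power is attached to no particular effect.

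At stake is whether the primary result can be interpreted. A reader cannot tell which test decides it or which effect the trial was built to detect. If 0.5 is meant as a non-inferiority margin, a failed test could be taken as evidence that interleaving is inferior when it only reflects low precision.

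**Working it through.** **Inputs.** From section 5.1: SD 1.1, one-sided alpha 0.025, power 0.80, threshold 0.5, 42 evaluable, 50 enrolled. From section 3.1: two equal parallel arms. Not stated: the true difference. I therefore use the *distance* between the true difference and the null boundary, and vary it.

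**1. The hypotheses, under each sign of the change score**

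| Meaning of change | Printed alternative (interleaving minus empirical at least 0.5) | Non-inferiority null with margin 0.5 |
|---|---|---|
| Larger change = improvement | interleaving better by at least 0.5 (superiority by a margin) | difference ≤ −0.5 |
| Follow-up minus baseline, lower score better | interleaving worse by at least 0.5 | difference ≥ +0.5 |

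Neither printed reading is non-inferiority. Under the first reading, with 20 per group, the probability of rejecting the printed null is 0.04% if the arms are equal and 29% if interleaving is truly better by 1.0 point; 80% needs a true benefit of 1.5 points.

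**2. Trying to reproduce 42**

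(Z0.975 + Z0.80)² = 7.849.

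- Printed formula, delta_1 = 0.5, sigma_d = 1.1: 7.849 × 1.21 / (2 × 0.25) = 18.99, so 19.
- Printed formula, sigma_d = 1.1 × √2 (the SD of a difference): 7.849 × 2.42 / 0.5 = 37.99, so 38.
- Usual two-sample formula at 0.5 points: 2 × 7.849 × 1.21 / 0.25 = 75.98, so 76 per group; noncentral t gives 77 (power 0.8003).

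None of these is 42. Two noncentral-t calculations do give it:

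- paired or crossover, sigma_d = 1.1, 0.5 points: power 0.79997 at a total of 40 and 0.820 at 42;
- parallel, SD 1.1, distance 1.0 point: power 0.79997 at 20 per group and 0.820 at 21 per group.

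The values are identical because σ²/(2δ²) = 2σ²/(2δ)²: the printed expression equals the two-sample formula at twice the distance. The first calculation does not fit the parallel design. The second needs an effect that the plan does not state, for example a 0.5 margin plus a 0.5-point true benefit.

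**3. Power of the parallel design** (noncentral t, SD 1.1, one-sided 0.025)

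| Per group | 0.5 | 0.75 | 1.0 | 80% reached at about |
|---|---|---|---|---|
| 20 (20% loss from 50) | 29% | 56% | 80% | 1.0 |
| 21 (42 evaluable) | 30% | 58% | 82% | 0.975 |
| 25 (no loss) | 35% | 66% | 88% | 0.89 |

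**4. Precision against a 0.5 margin**

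Half-width of the 95% CI = t × 1.1 × √(2/n):

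- n = 20: 2.024 × 0.348 = 0.70
- n = 21: 2.021 × 0.339 = 0.69
- n = 25: 2.011 × 0.311 = 0.63

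Each exceeds 0.5. To pass, the observed difference would have to favour interleaving by about 0.20, 0.19 or 0.13 points. This needs no assumption about the true effect, only an observed SD near 1.1.

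**5. Dropout**

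50 × 0.8 = 40, not 42. Keeping 42 of 50 is a loss of 1 − 42/50 = 16%. Starting from 42 with 20% loss, 42 / 0.8 = 52.5.

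**The case against.** The strongest reply is that the intent is clear and 42 is not arbitrary. Section 5.1 carries a non-inferiority heading, uses one-sided 0.025 and describes success as better or equivalent. A 0.5 margin with a 0.5-point true benefit, by noncentral t, gives exactly 21 per group. This stands as far as it goes: 42 may be right for an assumption that was never written down. It does not rescue the hypotheses. The decision rule repeats the same direction in words, so a slipped inequality sign does not explain it.

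Three stronger readings are tempting, and the documents do not support them.

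- *The trial has only about 30% power and needs some 150 patients.* The 29% to 35% figures and the 76 or 77 per group hold only at a distance of 0.5 points, for example a 0.5 margin with a true difference of zero. The plan does not state that distance.
- *The formula was taken from a crossover design.* It is compatible with one, but the algebra above shows that 42 cannot distinguish that origin from a parallel calculation at 1.0 point. The size of the formula's shortfall also depends on what sigma_d means.
- *Two-sided testing in section 5.2 contradicts the one-sided alpha.* It does not. Two-sided 0.05 and one-sided 0.025 share a critical value, and comparing a two-sided 95% CI with a margin is a standard non-inferiority analysis. The gap is that section 5.2 names neither the test nor the comparison.

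**Conclusion.** The point holds and should be corrected before analysis. The hypotheses contradict their label under either sign of the change score; this part rests on no assumption. The stated 42 and 80% do not follow from the stated method and inputs; this rests on the absence of a true difference and of symbol definitions. The number is undocumented, not shown to be too small.

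On size: with 40 evaluable patients and SD 1.1, 80% power is reached only about 1.0 point from the null boundary. All power and precision figures depend on the SD of 1.1, and the plan does not make clear which endpoint that SD describes.

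**What to change.** Keep 50 patients and change the wording of sections 5.1 and 5.2.

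1. **Hypotheses and test.** Define the sign of the change score. For non-inferiority, the null is that interleaving is worse by 0.5 points or more: interleaving minus empirical ≥ +0.5 if change is follow-up minus baseline, or ≤ −0.5 if change means improvement. If superiority is meant, drop the non-inferiority wording. Name the same test in section 5.2, for example the two-sided 95% CI compared with the margin.
2. **Formula.** Replace it with a parallel two-sample t-test calculation (noncentral t) and define each symbol. The form 2(Z+Z)²SD²/distance² may be shown as an approximation only: at 1.0 point it gives 19 per group, while the t-based answer is 21.
3. **True difference.** State it separately from the margin. If a 0.5-point benefit on top of a 0.5 margin was assumed, say so.
4. **SD.** Say which endpoint and visit the 1.1 belongs to. Section 5.1 sizes on the UPDRS IV total at month 12 but writes hypotheses for items 32 and 33.
5. **Power statement.** Suggested text: *With 40 evaluable patients (20 per group, 20% loss from 50), SD 1.1 and one-sided alpha 0.025, power by noncentral t is about 29% at 0.5 points from the null boundary, 56% at 0.75 and 80% at 1.0.* If 42 evaluable is kept, state the loss as 16%, with 30% at 0.5, 58% at 0.75 and 80% at about 0.975.

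The cost is wording only. The sponsor must commit to a sign convention, a margin and an assumed true difference, and accept that 80% power holds only at about 1 point from the null boundary.

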3.1 Randomization and masking

50 Patients will be randomly assigned to either the interleaving stimulation modes group (ISG) or the empirical stimulation modes group (ESG).

ISG: empirical stimulation for the first 3 months, followed by interleaving programming period for 6 months, and any stimulation decided by the neurologists/neurosurgeons for the final 3 months.

ESG: empirical programming for the first 9 months' period, followed by any stimulation decided by the neurologists/neurosurgeons for the final 3 months.

Patients are randomly assigned to receive either interleaving stimulation (interleaving group, 25 patients) or empirical stimulation (conventional group, 25 patients) after the enrollment, just before the implantation of the DBS device in the STN. The randomization ratio was 1:1 (Fig 1).

Randomization is done by computer-generated pairwise according to order of enrolment, so that similar numbers of patients are recruited to each study group. The chief investigator generates the randomization sequence. The randomization scheme is kept in sealed envelopes. The randomization sequence was revealed only to the unmasked clinician responsible for the stimulation programming, but not to the rater. Patients were masked to randomisation group.

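### Section 5.1 inflates 42 for 20% dropout by multiplying by 1.2 instead of dividing by 0.80, so 50 randomised gives 40 expected completers, not 42

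*Combined protocol and SAP*

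**What the plan says.** Section 5.1 names the method for comparing two independent means and reports its result: "42 subjects are planned to be enrolled in this study". The next sentence makes the allowance for attrition: "Increase the number of cases according to the 20% dropout rate, and finally enrolled 50 cases". Section 3.1 carries the inflated figure forward: "50 Patients will be randomly assigned to either the interleaving stimulation modes group (ISG) or the empirical stimulation modes group (ESG", with 25 patients per arm in a 1:1 ratio. The documents give no other dropout figure and no other inflation rule.

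The inputs in section 5.1 are a one-sided significance level of 0.025, power of 0.8, a threshold of 0.5 points in the hypotheses, and "Standard deviation of single group: SD = 1.1". The section also prints a sample-size formula whose denominator is twice the squared difference.

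**The concern.** A dropout rate is the share of enrolled patients who are lost, so the number to enrol is the required number divided by the share retained. Multiplying by one plus the rate always gives too few. Here the required number, the dropout rate and the enrolled number stand in adjacent sentences and do not agree.

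At stake is whether the trial has the cushion that section 5.1 implies. Someone reading it would expect 42 patients to remain after a 20% loss, and at that rate 42 would not be expected to remain.

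**Working it through.** **Inputs.** Required size 42, dropout 20%, enrolled 50, SD 1.1, difference 0.5, one-sided α 0.025, power 0.80 (all section 5.1); 1:1 allocation, 25 per arm (section 3.1).

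**Step 1: reproduce the plan's 50.**
- n × (1 + d) = 42 × 1.2 = 50.4. Rounded down, this is 50. Rounded up, it would be 51, or 52 for equal arms.
- n / (1 − d) = 42 / 0.80 = 52.5, so 53. Per arm, 21 / 0.80 = 26.25, so 27 per arm and 54 in total.

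The stated 50 therefore comes from the multiplicative shortcut and is 3 below 53 and 4 below 54.

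**Step 2: what 50 delivers.**
- Expected completers: 50 × 0.80 = 40, or 25 × 0.80 = 20 per arm if losses are equal. This is 2 short of 42.
- Largest dropout that leaves 42: 1 − 42/50 = 16%, which is 8 patients.

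**Step 3: where the 42 comes from.** With normal quantiles, (1.960 + 0.842)² ≈ 7.85, and the printed formula with SD 1.1 gives 7.85 × 1.21 / (2 × 0.25) = 18.99. That is 19 per group or sequence, 38 in total. With a t-test in place of the normal quantiles (noncentral t, N − 2 degrees of freedom, standard error 1.1/√N with N the total), power is 0.79997 at N = 40 and 0.820 at N = 42. So 42 is the smallest balanced total that reaches 0.80. A standard error of this form belongs to a crossover-type calculation.

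**Step 4: effect of losing two patients, on two bases.** The documents do not state the assumed true difference. I take 0.5 as the distance between the true difference and the boundary of the null hypothesis.

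| Calculation | Power, 42 in total | Power, 40 in total |
|---|---|---|
| Crossover-type, standard error 1.1/√N | 0.820 | 0.800 |
| Two parallel arms, standard error 1.1 × √(2/n), n per arm | 0.301 (21 per arm) | 0.288 (20 per arm) |

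On the parallel design the normal approximation needs 76 per arm, 152 in total, before any dropout allowance. After 20% dropout that becomes 152 / 0.80 = 190, whereas the × 1.2 shortcut would give 183 (152 × 1.2 = 182.4). The inflation rule would thus understate enrolment again once the base is recalculated.

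**The case against.** Four points can be made for the plan.

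- **The 20% could be meant as an uplift.** This would explain 50.4, but the text calls it a dropout rate, and an uplift would still round up to 51.
- **Dropouts are not necessarily lost to the analysis.** This partly stands. The Full Analysis Set in section 5.2 keeps patients who left early if they gave a usable post-baseline value, and the Per Protocol Set keeps those who quit for lack of effect. So 40 is the expected number of completers, and a reader who infers that exactly 40 will be analysed goes beyond the documents. The protection is limited: section 5.1 sizes the trial on a Month 12 change score, and section 5.2 gives no rule for a missing one.
- **Little power is lost.** This stands. The calculation that yields 42 has slack from rounding to equal groups and still gives about 80% at 40. A reader might infer that power falls from 80% to about 78%. That figure needs 42 to give exactly 80% in a parallel two-sample test, which implies a difference of 0.975. That difference appears nowhere in the documents; section 5.1 states 0.5.
- **A different base removes the shortfall.** The printed formula with normal quantiles gives 38, and 38 / 0.80 = 47.5, so 48, which 50 would cover. But the plan states 42, and its sentence must agree with that figure.

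**Conclusion.** The inflation step is wrong as written. Required size 42, dropout 20% and enrolment 50 are mutually inconsistent by 2 expected completers, or by 3 to 4 patients at enrolment. This needs only the plan's own figures and the ordinary meaning of a dropout rate.

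Its effect alone is small, about 2 percentage points of power on the crossover-type basis that reproduces 42. That basis is inferred from the printed formula and is not stated by the plan.

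A reader might also infer that enrolling 53 or 54 would secure 80% power. The documents do not support this. Sections 3.1 and 5.1 describe two parallel arms and two independent means, and on that design the stated inputs give about 30% power with 21 per arm and 29% with 20. The base calculation is the larger problem, and correcting the dropout step does not repair it.

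**What to change.** Keep 50 patients and restate the sentence in section 5.1 in one of two ways: *50 randomised with 20% dropout gives 40 expected completers (20 per arm)*, or *with 50 randomised, 42 completers are retained if dropout does not exceed 16% (8 patients)*.

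Do not attach a power figure to either sentence until the base calculation has been corrected. Any restated power should come from the parallel-arm calculation, with its difference, SD and significance level shown. If the required size is recalculated, divide it by 0.80 and round up to equal arms.

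The wording change costs one sentence and alters neither enrolment nor analysis. The accompanying correction of the base is not a small adjustment: with the present inputs, the power to be reported for 40 completers would be about 29%.
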